In this study, we will administer Fluzone® High-Dose vaccine with a planned booster to patients with monoclonal gammopathies irrespective of age versus a standard of care control group. Primary endpoint is composite of documented influenza infection rate and disease progression (as defined by International Myeloma Working Group criteria) at the end of the flu season. Based on the background data, we expect a higher rate of success in the experimental arm. As such, we power for success rates of 90% and 70% in the experimental and control arms, respectively. We will also analyze several secondary endpoints including rates of influenza related morbidity, the analysis of humoral and cellular immune response to these vaccines and the rate of disease control (defined as lack of disease progression by standard international myeloma working group criteria).

By comparing this experimental approach directly to standard of care, data from estimates of effectiveness will inform the design of larger future controlled studies. As such, the data from this study can lead to practice-changing results. The data on immune correlates will also yield important information about *in vivo* "immune-competence" of these individuals, which in turn is important to design trials with emerging immune therapies.

STUDY Endpoints:

Primary:

- 1) The primary clinical endpoint of this study is: to measure a composite of documented influenza infection rate and disease progression (as defined by International Myeloma Working Group criteria) at the end of the flu season following a high dose influenza vaccine booster strategy versus standard of care.

A Comprehensive Cancer Center Designated
by the National Cancer Institute

Phase: II

YCC Version 4.0 Date: 31-May-2017

pg. 8

Secondary:

1. evaluate rates of serologic protection (defined as HAI titer >40) following Fluzone® High-Dose influenza vaccine with booster dosing versus standard of care.
2. measure T cell subsets and flu-specific T cell responses following high dose influenza vaccine booster dosing strategy versus standard of care.

STUDY DESIGN:

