	Day of Initial Vaccine (Fluzone High Dose in experimental group A vs. standard of care in group B) Day of Initial vaccine, study enrollment and randomization into experimental versus standard of care arm	Day 7 (+/- 2 days) Research blood draw only*	Day of Second Vaccine (Fluzone High Dose in experimental group A vs. placebo booster in group B) Roughly 30 Days following Initial vaccine (+21 days/- 7 days)	Month 2 Roughly 30 Days following Second Vaccine (+14 days/- 7 days)	End of Study Visit ⁴ (may be conducted in person, by telephone, or by email) (End of flu season-May 1 to May 15, 2016)
SPEP OR IFE OR serum free light chains OR quantitative immunoglobulins ¹	X				X
Research blood draw ²	X	*X (patients may refuse this blood draw if it creates an unacceptable burden)	X	*X (if patients are unable to receive this blood draw within the above timeframe, blood draw may be delayed up to 90 days)	*X (patients may refuse this blood draw if it creates an unacceptable burden)
Inquire and document any influenza infection ³ , influenza-related hospitalization, or death during the study period	X		X	X	X
Assessment of all grade II and above adverse events ⁵			X	X	
Pregnancy test for women of childbearing potential ⁶	X		X		

¹ Assessment of disease status within 30 days prior to first vaccine and within 90 days of the End of Study Visit. Both patients with measurable or evaluable disease are eligible. The preferred method to monitor disease should be established at baseline and repeated at the end of study visit. For patients with measurable disease, SPEP or FLC are preferred.

² See Appendix A for details regarding collection of research samples and correlative studies.

³ All subjects should be informed and reminded to present to a health care facility at the first symptoms of possible influenza infection to have DFA checked.

⁴ End of treatment and 30 days following second vaccine may be merged into a single visit if they fall within 15 days of each other.

⁵ See Adverse Events section of the protocol for details.

⁶ Childbearing potential is defined as a sexually mature woman who 1) has not undergone a hysterectomy or bilateral oophorectomy and 2) has not been post menopause for at least 24 months. Pregnancy test to be performed within 2 weeks prior to each vaccine.

A Comprehensive Cancer Center Designated
by the National Cancer Institute

Phase: II

YCC Version 4.0 Date: 31-May-2017

pg. 11

Background and Rationale

Introduction

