Approximately 150 of subjects with monoclonal gammopathies will be screened for enrollment and must meet the eligibility criteria below. 100 patients will be randomized into the experimental group and 50 subjects will be randomized into the standard of care group. During screening, patients will be identified by disease type as having either disease requiring therapy or early disease. In order to maintain balanced stratification, patients of each disease type will be separately allocated in the same ratio of 2:1 experimental to control group. If a patient dies or discontinues their participation for any reason, we will not add another patient in their place.

Inclusion Criteria

Subjects must meet the following inclusion/exclusion criteria to be eligible for the study.

Inclusion criteria

1. Understand and voluntarily sign an informed consent form.
2. Age \geq 18 years at the time of signing the informed consent form.
3. Diagnosis of any monoclonal gammopathy: Monoclonal Gammopathy of Undetermined Significance (MGUS), asymptomatic / active multiple myeloma, asymptomatic / active Waldenström Macroglobulinemia (WM).

Exclusion criteria

1. Any serious egg allergy or prior serious adverse reaction to an influenza vaccine.

A Comprehensive Cancer Center Designated
by the National Cancer Institute

Phase: II

YCC Version 4.0 Date: 31-May-2017

pg. 17

2. Use of any other influenza vaccine for the 2015 to 2016 flu season.
3. Women who are pregnant or plan to become pregnant in the study period.

Visit schedule and assessments

Screening Assessments and all on study scheduled visits and assessments are outlined in Section 2 Table of Study Assessments.

At the end of the 2015-2016 flu season between May 1 to May 15, subjects will undergo off study evaluations per the Schedule of Assessments.

Vaccine Administration

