The principal investigator is responsible for monitoring the data, assuring protocol compliance, and conducting the safety reviews at the specified frequency [monthly]. During the review process the principal investigator will evaluate whether the study should continue unchanged, require modification/amendment, or close to enrollment.

The principal investigator, the Institutional Review Board (IRB), Yale Cancer Center Data and Safety Monitoring Committee (DSMC) have the authority to stop or suspend the study or require modifications.

This protocol presents minimal risks to the subjects and adverse events or other problems are not anticipated. In the unlikely event that such events occur, Reportable Adverse Events (which are events that are serious or life-threatening and unanticipated (or anticipated but occurring with a greater frequency than expected) and possibly, probably, or definitely related) or unanticipated problems involving risks to subjects or others will be reported in writing to the IRB (using the appropriate forms from the website) and any appropriate funding and regulatory agencies per IRB policy 710. The investigator will apprise fellow investigators and study personnel of all adverse events that occur during the conduct of this research project [via email as they are reviewed by the principal investigator.]

Biostatistical Considerations

The primary endpoint of this randomized Phase II study is a composite measure of two clinical endpoints. A patient is considered a treatment failure if either of the following events occur during the 2015-6 flu season:

- Progression of the underlying plasma cell disorder
- Any documented flu infection

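### A patient may be followed for progression by immunofixation alone, so a quantitative rise can go unseen and be scored as success in the primary endpoint

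*Combined protocol and SAP*

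**What the plan says.** The synopsis and the endpoints section make the primary endpoint a composite of documented influenza and "disease progression (as defined by International Myeloma Working Group criteria) at the end of the flu season". Biostatistical Considerations lists two events that make a patient a failure during the season; one is "Progression of the underlying plasma cell disorder". A patient with neither event is a success.

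The Schedule of Study Assessments has one row for disease status, marked at the day of first vaccine and at the end-of-study visit. It is met by "SPEP OR IFE OR serum free light chains OR quantitative immunoglobulins". Footnote 1 sets the time windows and adds three statements:

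- On who may enter, it says: "Both patients with measurable or evaluable disease are eligible".
- On consistency, it asks that whichever way of following the disease is chosen at the start be used again in May.
- On the choice of test, it says: "For patients with measurable disease, SPEP or FLC are preferred".

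The combined protocol and SAP does not say how a pair of IFE results is turned into progression or no progression, or how a patient whose progression status cannot be assessed is scored.

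**The concern.** SPEP, free light chains and quantitative immunoglobulins return amounts. IFE returns present or absent. A patient who is IFE-positive at baseline and still positive in May gives the same pair of results whether the protein fell, held steady or rose several-fold.

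Footnote 1 does not close this gap. The preference for SPEP or FLC is not binding and covers only measurable disease; no method is named for evaluable disease. The same-method sentence is sensible in itself, but if IFE is chosen at baseline it directs IFE again at the end.

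Failure is defined by events that occur, so a progression that the chosen test cannot show becomes a success unless routine care picks it up. The progression component, and the disease-control rate that the synopsis and background also plan to analyse, would then partly reflect which test the clinician chose. The synopsis says the estimates will inform larger trials; failure rates that are too low would carry over into their design.

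**Working it through.** **1. Can an IFE–IFE pair comply?** The row joins the four tests with OR, so IFE alone meets it. The SPEP/FLC sentence is a preference. The same-method sentence is satisfied by IFE twice. The pair therefore complies, including in a patient with measurable disease.

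**2. Inputs.**

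- 50 control and 100 experimental patients; success 0.70 and 0.90; stated power 0.93. Second example: 0.75 and 0.90, stated power 0.78 at significance level 0.1 (Biostatistical Considerations).
- Control failures: 20% influenza + 10% progression = 30% (Rationale for Treatment in this Setting).
- Pilot influenza rate under the experimental strategy: 2/51, about 4% (Background and Rationale).
- The plan does not split the 10% experimental failure rate into influenza and progression. Splits below are assumptions.

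**3. The plan's power.** Neither the test nor its sidedness is stated. A one-sided 0.10 test of two proportions with continuity correction comes close to both stated figures:

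z = [(p2 − p1) − 0.5(1/50 + 1/100) − 1.2816·SE0] / SE1

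SE0 uses the pooled proportion and SE1 the separate ones. For 0.70 against 0.90, the pooled proportion is (35 + 90)/150 = 0.8333, SE0 = 0.0645 and SE1 = 0.0714. So z = (0.20 − 0.015 − 0.0827)/0.0714 = 1.432 and power is 0.924 (stated 0.93). For 0.75 against 0.90, power is 0.793 (stated 0.78).

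**4. Expected progressions.** Control: 50 × 0.10 = 5. In the experimental arm, 4% influenza leaves 6% progression, or 6 patients, for a total of 11. Applying 10% progression to both arms gives 5 + 10 = 15, but that leaves no room for influenza in the experimental arm. A 5% + 5% split gives 10. The extreme of 10% influenza and no progression gives 5.

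**5. Progressions missed.** Let m be the share of progressions missed, an assumption. The number missed is 11m to 15m: 1.1 to 1.5 at m = 10%, 2.2 to 3 at 20%, 4.4 to 6 at 40%.

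**6. Effect on power.** With influenza rate f and progression rate p in the experimental arm, and the same m in both arms:

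- control success = 1 − 0.20 − 0.10(1 − m)
- experimental success = 1 − f − p(1 − m)

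| Experimental split (influenza + progression) | Power, m = 0 | m = 40% | m = 100% |
|---|---|---|---|
| 4% + 6% | 0.924 | 0.915 | 0.910 |
| 5% + 5% | 0.924 | 0.903 | 0.870 |
| 10% + 0% | 0.924 | 0.827 | 0.559 |
| 0% + 10% | 0.924 | 0.953 | 0.989 |

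For example, 4% + 6% with every progression missed gives success of 0.80 against 0.96 and power of 0.910. The loss is large only if nearly all experimental failures are influenza. If they are all progressions, power rises, because missing them removes failures that do not differ between the arms.

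**The case against.** The strongest reply is that the test menu is not the endpoint definition. Progression is defined by IMWG criteria, and Biostatistical Considerations counts progression during the season, by whatever means it is found. Routine care will detect some progressions, and IFE can itself show a protein that reappears. The SPEP/FLC preference is aimed at the measurable-disease patients at issue, and nothing suggests that IFE-only follow-up would be common. All of this stands and limits the number affected. It does not remove the gap: a compliant IFE pair may be the only scheduled evidence on a primary endpoint component.

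A reader might infer three stronger points, which the documents do not support.

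- **That footnote 1 sets an eligibility requirement which the inclusion criteria omit.** The sentence is permissive, saying that both categories are eligible. It does not contradict the inclusion criterion, which asks only for a diagnosis of one of the listed gammopathies. Copying it there would not help, since patients with evaluable disease only could still be followed by IFE.
- **That patients with non-secretory disease can enter and can never show progression.** The background introduces these disorders as ones whose plasma cells secrete monoclonal immunoglobulins, so the example is doubtful on the protocol's own terms.
- **That the comparison between arms is biased or the power clearly reduced.** The menu is the same in both arms, the trial is double blind, and the power results above move in either direction according to an assumed split.

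**Conclusion.** The point holds as a correctable weakness in how one component of the primary endpoint is ascertained. The schedule permits a qualitative test at both time points, and in a baseline-positive patient that test cannot show a quantitative rise. Undetected progressions are scored as success.

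Progression supplies 10 of the 30 points of planned control failure, one third. The expected effect is non-differential under-counting of progression and an inflated disease-control rate in both arms. The number affected cannot be derived from the documents. It rests on an assumed total of about 11 to 15 progressions (fewer under other splits), on the unknown share followed by IFE alone, and on how many of those routine care would catch. The case for change rests on the validity of the measurement, since a loss of power is not established. The IMWG thresholds are not reproduced in the documents, and nothing here depends on them.

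**What to change.** In footnote 1, replace the preference with a rule:

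- Every patient with a quantifiable M-protein or light chain at baseline has the same quantitative test at baseline and at end of study. That test is SPEP or serum FLC, or quantitative immunoglobulins where that is the marker being followed.
- IFE alone is accepted only when baseline IFE is negative and no quantifiable marker exists. There, conversion to positive is informative.

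The inclusion criteria need no change.

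This version is dated 31 May 2017, after the end-of-study window of 1 to 15 May 2016, so the data may already be collected. In that case, list the baseline and end-of-study test pairs by arm, and repeat the primary analysis in patients with paired quantitative tests as a sensitivity analysis.

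The cost is one footnote. The tests are already on the menu and no visit is added. The clinician loses some choice of test. The sensitivity analysis would use fewer patients and would be less precise.

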Ultimately if this novel vaccine strategy proves to be more effective, an important question will be if mortality will also be improved. As discussed above influenza infections are associated both with their own morbidity and mortality, and may have a negative impact on disease control, thereby indirectly increasing mortality. All-cause mortality as a clinical endpoint will take into account all possible relation of influenza infections to mortality. One year estimates are known for patients with plasma cell disorders. The most recent SEER data of one year survival for newly diagnosed myeloma, based on patients diagnosed in 2009 is 79.2%.¹⁷ Relapsed refractory patients have lower survival depending on many risk factors and is estimated as low as 60-66%.^{18,19} MGUS patients are not believed to have much of a decrease in survival compared to age-matched controls and one-year survival is estimated to be 98%.²⁰ Most of the patients seen at Smilow cancer Hospital are relapsed/refractory multiple myeloma patients. We anticipated that more than 2/3 of patients enrolled will be relapsed / refractory and less than 1/3 will be MGUS or newly diagnosed plasma cell disorder patients. As would be expected, relapsed patients have reduced time to progression with each successive line of therapy. Kumar, et al²¹ followed 355 myeloma patients who have had at least two lines of therapy and showed that time to progression shortened with each line of therapy from 9.9 months after first therapy to 7.3 months after second therapy to less than 4 months after sixth line of therapy (see Figure 1 below). In our population of patients of relapsed patients mixed with newly diagnosed and early disease patients a conservative estimate of the proportion who would relapse from the time of initial vaccine to the end of the influenza season (which may range from roughly 4-8 months depending on when the patient receives their initial vaccine) is 10%. Considered together with an expected influenza infection rate of 20%, we would expect our control arm to have a combined disease progression and influenza infection rate of 30% (10%+20%).

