We plan to enroll 50 patients in the standard care group and 100 in the vaccine group for a total of 150. Patients will be separately allocated in this 1:2 ratio based on their disease type of early disease versus active disease in order to maintain balanced stratification between the groups. For each disease type, this 1:2 ratio will be performed in blocks of three in order to maintain balance in the study at all times. A randomization schedule will be prepared by the study biostatistician, [name], in advance of the trial beginning. If the standard care group has 0.70 probability of success (defined above) and the vaccinated group has probability of success equal to 0.90 then the power of this design is 0.93. As another example, if the standard care group has 0.75 probability of success and the vaccinated group has 0.90 probability of success then the power of

A Comprehensive Cancer Center Designated
by the National Cancer Institute

Phase: II

YCC Version 4.0 Date: 31-May-2017

pg. 21

our design is 0.78 at significance level 0.1. Patient deaths which are not related to influenza or disease progression will be censored for efficacy analysis.

Yale University's online OnCore system will be used to randomize the patients. Randomization will be performed by the clinical trials office of Yale University and the information released only to the research pharmacist.

We will monitor the study for the toxicity of the vaccine. The unacceptable toxicities include any serious adverse event grade 3 or higher which is believed to be related to the study vaccine. The tolerability will initially be tested in the first 20 patients in the vaccine arm. We will consider the vaccine tolerable if the rate of vaccine related toxicity is 10% or less and intolerable if 30% or more. If, in the first 20 patients, we observe 5 or more patients with vaccine related toxicity, then the cohort will be terminated early. With this design, the probability of terminating the cohort early is 0.04 if the true but unknown toxicity rate is 10% and 0.76 if the true rate is 30%.

Regulatory Considerations

Institutional Review Board/Ethics Committee approval

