Appendix B – Figures and Tables

*Figure 1: Gradual decrease in the response duration of myeloma patients with increasing order of treatment regimen

*Figure from Kumar, et al. Mayo Clin Proc 2004. Response duration is defined as time to death or start of a new therapy.

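### Progression at any time in the season counts as failure, but disease is assessed only at baseline and near season end, so interim progression may be missed

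*Combined protocol and SAP*

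**What the plan says.** The rule for the primary endpoint is in Biostatistical Considerations: "A patient is considered a treatment failure if either of the following events occur during the 2015-6 flu season", the two events being progression of the plasma cell disorder and documented influenza. This is an any-time rule. The synopsis, the Rationale for Treatment and the Primary endpoints section instead place the composite at the end of the flu season, which can be read as status at that point.

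The Schedule of Study Assessments marks the disease tests (SPEP, IFE, free light chains or immunoglobulins) in two columns only, initial vaccine and End of Study. Footnote 1 sets the timing: "Assessment of disease status within 30 days prior to first vaccine and within 90 days of the End of Study Visit". It adds that the monitoring method is fixed at baseline and repeated at the end. The End of Study Visit may be held by telephone or email.

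The inquiry row, marked at four visits, covers influenza, influenza-related hospitalization and death. Under Adverse events, collection after the 30-day booster window is limited to survival, influenza-like illness and documented influenza. Neither place mentions progression or change of therapy.

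On the population, the rationale states: "We anticipated that more than 2/3 of patients enrolled will be relapsed / refractory". It plans 10% progression and 20% influenza in the control arm, over roughly 4 to 8 months. Appendix B notes, for the figure cited beside the progression estimate: "Response duration is defined as time to death or start of a new therapy".

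**The concern.** The failure rule needs to know whether progression occurred at any point between first vaccine and May. The data plan tells the analyst only how the disease stood at two points. Eligibility places no restriction on anti-myeloma treatment, and most patients are expected to be relapsed or refractory, so changes of regimen during the season are foreseeable. A patient who progresses in the autumn, changes regimen and responds can have a late value no worse than baseline. Nothing in the schedule would reveal the event.

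The two wordings add to the problem. Someone following the schedule and the end-of-season wording could score this patient a success, while someone who consulted the chart and applied the any-time rule would score a failure. Progression accounts for one third of the planned control failures (10 of 30 percentage points), so the classification should not depend on who looks where. The 90-day allowance also means that the second assessment can precede the May visit by up to three months, so a late progression could be missed too.

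**Working it through.** **1. The plan's own power.** Inputs from Biostatistical Considerations: "We plan to enroll 50 patients in the standard care group and 100 in the vaccine group for a total of 150"; success 0.70 against 0.90; level 0.1. Sidedness is not stated.

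Power = Φ(|p1 − p2| / SE − 1.645), with SE = √[p̄(1 − p̄)(1/50 + 1/100)].
- 0.70 vs 0.90: p̄ = (50 × 0.70 + 100 × 0.90)/150 = 0.833; SE = 0.0645; 0.20/0.0645 = 3.098; Φ(1.453) = 0.927. The plan says "then the power of this design is 0.93".
- 0.75 vs 0.90: p̄ = 0.85; SE = 0.0618; 0.15/0.0618 = 2.425; Φ(0.781) = 0.782. The plan says "our design is 0.78 at significance level 0.1".

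Both figures reproduce with a pooled standard error at two-sided 0.10 (equivalently one-sided 0.05).

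**2. Share of progressions early enough to be reversed by May.** Inputs: median 7.3 months, the rationale's figure after second therapy; 6 months of follow-up, the middle of 4 to 8. Assumptions: constant hazard, and 3 months to switch and respond.
- F(t) = 1 − 2^(−t/median)
- F(6) = 0.434; F(3) = 0.248
- Share at least 3 months before the end = 0.248/0.434 = 0.571

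**3. Share of progressions missed.** Assume 30% to 60% respond to the new regimen (not in the documents) and no chart information is used.
- 0.571 × 0.30 = 0.171; 0.571 × 0.60 = 0.342
- Median 9.9 months, 4 months of follow-up: share 0.277, missed 0.083 to 0.166
- Median 4 months, 8 months of follow-up: share 0.773, missed 0.232 to 0.464

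**4. In patients, at the protocol's 10% progression.**
- 10% × 0.171 = 1.7 points; 10% × 0.342 = 3.4 points
- Control arm: 5 expected progressions in 50 patients, of which 5 × 0.171 = 0.9 to 5 × 0.342 = 1.7 are missed
- Over the wider range in step 3: 0.8 to 4.6 points

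The 7.3-month median implies 43% progression at 6 months, well above 10%. With the hazard set to give 10% at 6 months instead, F(3) = 1 − √0.90 = 0.0513 and the share is 0.513. Missed progressions are then 0.154 to 0.308, or 1.5 to 3.1 points. The result hardly depends on this choice.

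**5. Effect on power.** Remove equal shares of progressions from both arms, using the formula in step 1. The documents do not say how the experimental arm's 10% failures divide, so three splits are shown.

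| Experimental split (progression + influenza) | 17.1% missed | 34.2% missed | 100% missed |
|---|---|---|---|
| 5% + 5% | 0.920 | 0.914 | 0.893 |
| 6% + 4% | 0.926 | 0.925 | 0.937 |
| 10% + 0% | 0.944 | 0.961 | 0.999 |

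Against 0.927 with full capture, power falls slightly, barely changes, or rises.

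**The case against.** The strongest reply is that the operative rule already covers this patient. Progression during the season is a failure, later response does not cancel it, and nothing says that progression is judged solely by comparing two values. A reader might infer from the schedule that such a patient is always scored a success. The documents do not support that: a progression known from routine care should count as failure. What stands is that no source for that knowledge is named and no data item records it.

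A reader might also infer that a treatment switch after an influenza-related interruption would be hidden. For documented influenza it would not, because influenza alone makes the patient a failure and it is asked about at four visits.

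A third inference is that the observed progression rate cannot be compared with the planning rate, because the cited figure counts start of new therapy as an event. The 10% is presented as a conservative judgment for a mixed population and is not calculated from that figure, so this cannot be shown.

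Finally, one could apply the 7.3-month median to two thirds of patients: 2/3 × 0.434 = 29% progressing, and 29% × 0.171 to 0.342 = about 5 to 10 points missed. That sets aside the protocol's own 10%, so it is not used here.

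**Conclusion.** The point holds as an ascertainment gap. The endpoint rule counts events that the data plan does not collect, and two wordings of the endpoint allow different classifications of the same patient. Mid-season progression followed by response may be missed and counted as success.

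The failure rate would be understated by roughly 1.7 to 3.4 percentage points at 10% progression. This is conditional on a 7.3-month median, 6 months of follow-up, a constant hazard, 3 months to switch and respond, 30% to 60% response and no use of chart data. The true frequency cannot be derived from the documents.

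A reader might infer a loss of power. The calculation does not establish one: the direction depends on a split of experimental-arm failures that the plan does not give. The harm is an understated failure rate and a composite that differs from its definition.

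**What to change.** - In the synopsis, rationale, endpoint and biostatistics sections, use one definition: IMWG progression at any time from first vaccine to end of season.
- Add to the existing inquiry row of the schedule, at each visit: progression or change of anti-plasma-cell therapy, with date and reason.
- Abstract interim routine SPEP and free light chain results from the chart before unblinding, and count any IMWG progression documented there as failure.
- Use start of a new therapy for progression as a prompt to look for IMWG progression, or in a sensitivity analysis. It need not be a separate failure event, since that would add a treatment decision to a criteria-based endpoint.

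The cost is protocol and case report form wording plus chart abstraction, with no added visits or tests. The current version is dated after the 2015-6 season, but routine results can still be abstracted retrospectively. A small downside is that routine monitoring frequency differs between patients, so detection will be uneven, but it is blind to arm.
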